5.4 Primary Outcome Measure

Community ambulation is a construct that includes the ability to accommodate change in level and terrain irregularity (necessary to enter and leave the home and for curb management), avoid obstacles and walk a requisite distance.¹⁰⁶ Compared to older adults who are active in the community, persons with a mobility disability do not travel alone, take fewer trips and perform fewer activities per trip, walk shorter distances, cross the street less often, carry fewer

objects, and have fewer postural transitions (turning the head, extending their reach, or changing direction).¹⁰⁷ Although community ambulation is complex, covering a minimal distance within a specified period of time is a critical feature.^{108,109}

[figure not shown]
The SMWT is a standardized test that examines both the distance and time components of community ambulation.¹¹⁰ The Cardiovascular Health Study¹¹¹ concluded that the SMWT is safe for use in community samples to measure the impact of multiple comorbidities on endurance in older adults.²² Harada et al¹¹² proposed that the SMWT is a useful integrated measure of mobility function taking into account any limitations imposed by major body systems.¹¹² Lord and Menz¹¹³ concluded that the SMWT provides a measure of overall mobility and physical function in addition to being a measure of cardiovascular fitness. Sixty-nine percent of the variance in the SMWT is explained by physical functioning, lower body strength, standing balance, and gait speed.¹¹² Construct and predictive validity and responsiveness to change were established for the SMWT in a sample of 108 persons with hip fracture.¹¹⁴ A high positive correlation was reported between pedometer-determined physical activity and the SMWT test suggesting that both are correlates of community ambulation.¹¹⁵ The SMWT also has been used as an outcome measure to determine the effectiveness of exercise interventions for elderly patients with and without hip fracture.^{20,56,116} In addition to the distance walked in six minutes, gait speed will also be derived. The primary end point for this pilot study is the total distance walked in six minutes.

Section 6: Study Design

6.1 Overview of Study Design

A pilot study including 30 older adults who have experienced a hip fracture will be carried out with participants receiving a specific multi-component intervention with protein supplementation (PUSH Plus Protein). Study activities for participants meeting eligibility criteria will take place after post-acute rehabilitation ends, up to 26 weeks after admission to the hospital for hip fracture. Patients age 60 and older who have had surgical repair for hip fracture will be identified in study hospitals or by self-referral and evaluated for eligibility. Following consent to participate, eligible participants will undergo a comprehensive baseline assessment. Participants completing the baseline assessment will be eligible to receive the intervention. All participants will receive the PUSH Plus Protein intervention. The follow-up assessment will occur after the intervention is completed, approximately 16 weeks after baseline testing. Figure 1 shows the sequence of participant contacts from the time of hospitalization until the 16-week assessment.

Figure 1. Timeline for screening and follow-up

Within a week of complete baseline testing, the physical therapist (PT) will initiate the exercise intervention and the protein supplement in the home setting. Participants will also receive counseling with a registered dietitian. The follow-up assessment will take place 16 weeks after baseline testing. Telephone interviews will be conducted every four weeks, beginning four weeks after baseline testing, to obtain information about RAEs and expected AEs, and to help reduce loss to follow-up by maintaining ongoing rapport with participants. An honorarium will be given at the completion of both study assessment visits.

6.2 Interventions

Over a 16-week period, participants will receive two visits per week from a study PT, on non-consecutive days, for a total of 32 visits. These visits will take place in participants' place of residence. Participants will be given a whey-based protein supplement containing 27.6g of protein to be taken daily. Participants will also receive 2,000 IU of vitamin D3, 600 mg of calcium, and a multivitamin daily during the 16-week study period and counseling with a registered dietitian to ensure body weight stability and adequate nutrient intake inclusive of a healthy diet.

Section 7: Selection and Enrollment of Participants

7.1 Eligibility

Participants will be evaluated for eligibility in three phases (see Figure 2), all of which must be completed no more than 26 weeks after admission to the hospital for a hip fracture. In phase 1, patients will be assessed for inclusion criteria and medical exclusions. Information for phase 1 will be collected from the patient's medical chart. A HIPAA Partial Privacy Waiver (for recruitment) or verbal consent to review the medical chart for eligibility will be obtained for patients who are identified at study hospitals up to 26 weeks after their admission for hip fracture; this includes patients who were admitted to the hospital for hip fracture up to five months prior to the start of screening.

Patients who are provisionally eligible based on medical chart review at phase 1 will be approached or contacted by telephone to be told about the study in the hospital or after discharge (up to 26 weeks after admission for hip fracture). Interested patients who are approached in the hospital or rehab will be asked to provide written Permission to Contact for additional screening. If we are unable to get written Permission to Contact while the patient is still in the hospital, we will contact patients via telephone to determine their interest in the study and obtain verbal Permission to Contact for additional screening. Patients who are identified through other means of recruitment (e.g., patients who call the study office in response to advertising or physician referral) will undergo a brief pre-screening over the telephone. Potentially eligible patients who are interested in participating will be asked to provide written authorization for release of medical records for review of phase 1 eligibility criteria. Those who agree to further contact will be screened in phase 2 to assess for medical, safety, and feasibility criteria. Informed consent must be obtained prior to any further data collection or research procedures beyond phase 1 screening criteria.

Blood will be collected and tested for hemoglobin (<9 g/dl), serum creatinine to calculate creatinine clearance (<15 ml/min or 15-29 ml/min), serum albumin (<2.5 g/dl), and hemoglobin A1c level (>10%). The blood collection can occur anytime between phases 2 and 3 screening as long as it occurs after informed consent is obtained and no more than 4 weeks prior to baseline testing.

[figure not shown]
Phase 3 will assess final eligibility at the clinical site center at the beginning of the baseline visit. Phase 3 must be completed no later than 26 weeks after admission to the hospital for hip fracture. Phase 3 will include a review of all disqualifying medical conditions, assessment of cognitive status with the Modified Mini-Mental State examination (3MS), and evaluation of ability to walk 300 meters in six minutes. This final test will be used to exclude participants who are unlikely to benefit from the study interventions because their gait speed is very low (<0.1 m/s) and to exclude those who are able to walk 300 m or more in six minutes and are, therefore, already classified as community ambulators. The study physician must review all study eligibility documents and sign off on final eligibility for all potential participants prior to collection of baseline data. All participants will be seen by the study physician.

Eligible individuals will receive the baseline assessment consisting of questionnaire items, DXA and CT scans, and testing of strength, balance and functional performance.

7.1.1 Required Baseline Data

Certain components of the baseline assessment must be completed by all participants in the pilot study in order to make useful comparisons to data from participants in CAP and CAP-MP and to have enough power to achieve primary and secondary research aims. Participants who perform the required components (identified in Section 10: Study Procedures) no later than 26 weeks after hospital admission for the hip fracture will be said to have complete baseline data and thus be eligible to receive the PUSH Plus Protein intervention.

Figure 2. Algorithm for Screening

7.2 Inclusion Criteria (Target Population)

1. Minimal trauma, non-pathologic hip fracture with surgical repair
 - 1.1 Closed fracture of proximal femur
 - 1.2 Minimal trauma fracture
 - 1.3 Surgical fixation of fracture
 - 1.4 Non-pathologic fracture
2. Age 60 or older
 - 2.1 Age 60 or older at time of baseline testing
3. Community ambulation
 - 3.1 Living in the community at time of fracture
 - 3.2 Ambulating without human assistance two months prior to fracture
 - 3.3 Unable to walk 300 m or more in six minutes without human assistance at time of baseline testing

7.3 Exclusion Criteria

4. Logistical impediments to participation
 - 4.1 Does not live within reasonable distance of the clinical center
 - 4.2 Participant plans to move out of area or otherwise be unavailable during the 16-week intervention period
 - 4.3 Participation in another clinical trial
 - 4.4 Not English speaking
 - 4.5 Baseline testing not completed by 26 weeks post admission for hip fracture
 - 4.6 Final sign off from study physician and/or principal investigator is incomplete
 - 4.7 Incomplete baseline data
 - 4.8 Unable to contact participant
 - 4.9 Participant is unable to provide her/his own informed consent
 - 4.10 Participant refuses the study
5. Medical impediments to participation or low potential for benefit from interventions
 - 5.1 Calculated creatinine clearance < 15 ml/min
 - 5.2 Serum albumin < 2.5 g/dl

- 5.3. End stage renal disease on dialysis (CKD stage 5 or 6)
- 5.4. Lower extremity amputation
- 5.5. Cognitive impairment (3MS score <73)
- 5.6. Severely diminished lower extremity sensation or ulceration
- 5.7. Participant walks less than four meters in 40 seconds (<0.1 m/sec)
- 5.8. Not community-residing (e.g., resident of a skilled nursing facility) at time of baseline testing
- 5.9. Receiving PT for the hip fracture in the hospital or in an inpatient rehabilitation facility at time of baseline testing

- 6. Medical contra-indications for exercise
 - 6.1. Hemoglobin < 9 g/dl
 - 6.2. Symptoms of angina pectoris
 - 6.3. Recent myocardial infarction
 - 6.4. Uncompensated congestive heart failure
 - 6.5. Chest pain or shortness of breath (including from severe chronic obstructive pulmonary disease)
 - 6.6. Uncontrolled hypertension
 - 6.7. Not fully weight-bearing on fractured leg or non-fractured leg at time of baseline testing
 - 6.8. Study physician thinks participant is not a good candidate for study (e.g., not likely to survive study period)
 - 6.9. Development of chest pain or substantial shortness of breath or ambulating with severe pain during baseline SMWT

- 7. Medical contra-indications for whey protein supplement
 - 7.1. Chronic kidney disease (CKD stage 4)
 - 7.2. Severe liver disease (e.g., hepatitis, fatty liver disease, cirrhosis)
 - 7.3. Hemoglobin A1c level > 10%
 - 7.4. Known dairy allergy
 - 7.5. Known celiac disease
 - 7.6. Known history of severe, life-threatening peanut or shellfish allergy
 - 7.7. Calculated creatinine clearance 15-29 ml/min

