The research is based on the premise that successful community ambulation requires certain factors that are influenced by underlying physical or chemical processes. The key factors include endurance, walking speed, muscle strength, balance, lower extremity function, skeletal integrity, and fracture healing. We believe that physical activity and protein supplementation can impact these factors to improve the ability to walk. We want to gain a better understanding of which factors play a role by performing tests that measure physical function, strength, balance, level of inflammation, bone turnover rate, muscle density, and body composition.

Participant data from this pilot study will be compared to data from participants who received the PUSH intervention without protein in two recently completed studies: 1) Community Ambulation Project (CAP parent study) and 2) Community Ambulation Project- Mechanistic Pathways (CAP-MP ancillary study).

Study Title

PUSH Plus Protein Pilot Study for Hip Fracture Patients (hereafter referred to as PUSH Plus Protein)

Objectives

The primary outcome will be to test whether the PUSH Plus Protein intervention improves community ambulation (as measured by distance walked in six minutes) compared to PUSH intervention alone (from CAP study) at the end of 16 weeks. The effects of PUSH Plus Protein on precursors to community ambulation compared to the PUSH intervention alone (CAP study) and the effects of PUSH Plus Protein intervention on the mechanistic factors compared to PUSH intervention alone (from CAP-MP study) will also be examined. In addition, the safety and tolerability of delivering the PUSH Plus Protein intervention to hip fracture patients will be assessed.

Design and Outcomes

In addition to providing important information on adherence, feasibility, and safety, this pilot study of 30 hip fracture patients has the unique advantage of being able to compare data to two recently completed studies where participants received the PUSH intervention without protein supplementation described below.

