3.1.5 UMB Investigational Drug Services (IDS)

The University of Maryland IDS is responsible for the purchasing, distributing, and accounting procedures for all investigational drugs within the University of Maryland Medical Center campus and will be responsible for preparing the vitamins/supplements for this project. The vitamins/supplements for the study will be purchased and packaged through the University of Maryland IDS. IDS will prepare “treatment kits” for each participant who receives the intervention that will include all vitamins/supplements for the 16-week study period:

- 1.) 2000 IU vitamin D3, one tablet daily
- 2.) 600 mg calcium, one tablet daily
- 3.) Multivitamin, one tablet daily

Each treatment kit will contain four individual packs numbered 1-4. Each pack contains a 4-week supply of vitamin D3, calcium, and a multivitamin. The IDS will prepare appropriate packaging for each item in the treatment kit, with a label and directions for taking each product that complies with legal requirements. Participants who have contraindications for calcium supplementation (i.e., calculated creatinine clearance < 30 ml/min, elevated total or ionized calcium, history of kidney stones, primary hyperparathyroidism, or sarcoidosis) will not be given calcium.

Protein powder will be ordered by the study and shipped directly to IDS for labeling. The IDS will prepare appropriate labeling for each container of protein powder that complies with legal requirements. Each participant will receive four 2 lb. containers of protein powder numbered 1-4. Each container is a 30-day supply of protein powder.

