4.1 Primary Objective

The purpose of this study is to test whether adding a protein supplement to the PUSH intervention (PUSH Plus Protein) initiated up to 26 weeks post admission leads to greater improvement in a person's ability to walk in their own home and in the local community 16 weeks after study entry compared to the PUSH intervention alone; therefore, data in this pilot study will be compared to data from participants in the CAP study across the three sites who received the PUSH intervention alone (n=105). Our working hypothesis is that PUSH Plus Protein will lead to greater improvements in ability to walk in the community compared to PUSH.

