14.1 Primary Aim

The primary aim is to compare the PUSH Plus Protein study subjects (n=30) to those who received PUSH from CAP (n=105). The primary outcome is the distance walked in six minutes (6MWT). Previous analyses of various physiologic measures in the Baltimore Hip Studies data ("BHS"; data unpublished) have shown a $r>0.80$ within subject correlation of measures across time. Preliminary data from CAP-MP have shown a within subject correlation of $r=0.78$ for initial subjects in usual walking speed (n=13).

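### The pilot screens out people with whey contraindications, but nothing in the plan applies the same screen to the external PUSH-only controls

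*Protocol*

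**What the plan says.** **Pilot entry.** Protocol 7.3 sets apart a list headed "Medical contra-indications for whey protein supplement". Its seven items are stage 4 chronic kidney disease (7.1), severe liver disease (7.2), HbA1c above 10% (7.3), dairy allergy (7.4), celiac disease (7.5), severe peanut or shellfish allergy (7.6) and "Calculated creatinine clearance 15-29 ml/min" (7.7). Section 11.1.5 explains these exclusions as safety measures for the protein powder.

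**Comparator.** Section 14.1 and the SAP's Primary Aim set out to "compare the PUSH Plus Protein study subjects (n=30) to those who received PUSH from CAP (n=105"). The Executive Summary describes the controls as "participants who received the PUSH intervention without protein in two recently completed studies". For outcomes measured only in CAP-MP, the comparator is 19 PUSH participants.

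**Analysis.** The GEE in 14.2 and the SAP (Secondary Objectives) contains group, time and their product, with no baseline covariates. The weights in 14.3 model the probability of being observed at follow-up. Marginal structural modelling is mentioned as something that could be combined with those weights, but no such model is specified.

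**Sample size.** Section 14.4 takes the effective control number as 105 less 10% attrition, so no allowance is made for controls removed on eligibility grounds.

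**The concern.** With an external control group, the first requirement is that both groups could have met the same entry rules. Here one set of rules exists because of the whey powder, which the controls never received. If CAP enrolled people with advanced renal disease, severe liver disease or HbA1c above 10%, they sit in the control group with no counterpart in the protein group. Any smaller recovery among them would then be credited to protein, which is the direction of the working hypothesis. The pilot is also meant to inform the size of a definitive study, so an inflated effect would carry forward.

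If the entry rules do differ, covariate adjustment is a weak remedy. No pilot participant would have clearance 15-29 ml/min, so a regression would extrapolate and weighting would lack overlap. Restricting the controls deals with the problem directly.

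**Working it through.** **Did CAP apply list 7?** The documents do not give CAP's criteria. The indirect evidence is:

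- The list is headed and justified as whey-specific, and CAP gave no whey.
- Renal function is split. Clearance below 15 ml/min is a general exclusion (5.1), while 15-29 appears only under whey (7.7). Section 7.1 repeats the two bands.
- Sections 3.1.5 and 11.1.7 withhold calcium at "calculated creatinine clearance < 30 ml/min". Under 5.1 and 7.7 together nobody below 30 can enter the pilot, so the renal part of that rule applies to no one here. It would have a use in a study that enrolled people at 15-29.
- Other CAP text survives: three study sites in Section 1 and 8.2 of a single-site study, and CAP named as the body accessing records in 11.2.

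This is fairly strong for renal function and weaker for liver disease and HbA1c, where only the heading speaks. Items 7.4-7.6 have no evident link to walking recovery.

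**Reproducing the plan's figure.** Inputs from 14.4: 94 v 27, r = 0.70, two-sided alpha 0.05, 80% power. For change scores:

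(1.960 + 0.842) x sqrt(1/94 + 1/27) x sqrt(2 x (1 - 0.70)) = 2.802 x 0.2183 x 0.7746 = 0.474 SD

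The plan states 0.475. With SD 55.8 m this is 0.475 x 55.8 = 26.5 m. Section 14.4 prints 22.9 m, which is 0.41 x 55.8. That mismatch is a separate matter, and I use 26.5 m as the yardstick.

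**Size of a possible bias.** Let p be the share of controls who would fail list 7, and d the shortfall in their mean 16-week change. The control mean change is lowered by p x d, so b3 is raised by p x d. Neither input is in the documents. Assume p = 5-15% and d = 20-40 m:

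- Low: 0.05 x 20 = 1 m, 4% of 26.5 m
- High: 0.15 x 40 = 6 m, 23% of 26.5 m

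The standard error of b3 is 55.8 x 0.7746 x 0.2183 = 9.4 m. A bias b makes the true two-sided error 1 - Phi(1.96 - b/9.4) + Phi(-1.96 - b/9.4): 5.1% at 1 m, 5.5% at 2 m and 9.7% at 6 m, against a nominal 5%.

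**Cost of filtering the CAP controls** (share removed is assumed, then 10% attrition, rounded down):

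| Removed | Effective controls | Detectable difference | Power at 0.475 SD |
|---|---|---|---|
| 0% | 94 | 0.474 SD (26.4 m) | 80.2% |
| 10% | 85 | 0.479 SD (26.8 m) | 79.3% |
| 15% | 80 | 0.483 SD (27.0 m) | 78.7% |
| 30% | 66 | 0.496 SD (27.7 m) | 76.6% |

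The loss is small because the 27 pilot participants dominate the variance (1/27 = 0.037 against 1/94 = 0.011).

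**CAP-MP.** The stated 0.62 SD reproduces at 17 v 27 with a baseline-adjusted variance: 2.802 x sqrt(1/17 + 1/27) x sqrt(1 - 0.70^2) = 0.620. If two of the 19 were removed (assumed), 17 x 0.9 leaves 15, and the same formula gives 0.644 SD. The cost is larger here but still modest.

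**The case against.** The strongest objection is that CAP's and CAP-MP's criteria and case mix are absent from the documents. A reader might infer that the protein group has been pre-selected to be healthier, or that people with clearance 15-29 ml/min exist in one group only. The documents support neither as fact. Both need CAP to have admitted such people and some of them to be among the 105. The calcium rule could equally be a standing supplement-safety list, and it bears only on renal function.

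Three further points stand:

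- List 7 is not a general health filter. Three of its seven items concern allergy or celiac disease, and 7.1 and 7.7 overlap.
- b3 compares change from baseline, so a fixed deficit in walking distance cancels. Bias arises only if these patients' 16-week change differs, which is plausible but not documented. The assumed 20-40 m shortfall is itself 75-150% of the 26.5 m detectable difference, and at the low end the bias is about a tenth of a standard error.
- Restriction works only for criteria that CAP recorded, so it may align the groups only in part.

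It is also fair to say that this is one facet of using a non-randomised, three-site, earlier comparator for a single-site pilot that has feasibility and safety aims too.

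None of this answers the narrower point. The plan neither shows that the entry rules match nor says what happens if they do not, although 7.1.1 and 10.1 make some baseline measures mandatory precisely so that comparisons with CAP and CAP-MP are useful.

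**Conclusion.** The concern holds in conditional form. It is documented that the pilot applies list 7, that all 105 CAP PUSH participants (and 19 from CAP-MP) serve as controls without a filter, and that the model has no covariates. It is inferred, well for renal function and less well for liver disease and HbA1c, that CAP did not apply the list. It is presumed that any bias favours protein.

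The size cannot be found from the documents. The 1-6 m range rests wholly on the assumed 5-15% share and 20-40 m shortfall, and it is zero if CAP used equivalent exclusions or if those patients change as much as the others. This does not invalidate the comparison. It is a gap that can be closed cheaply, and applying the pilot's own health-related entry rules to its controls is a better-founded primary comparison than taking all 105.

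**What to change.** In Protocol 14.1 and the SAP's Primary Aim:

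1. State the CAP and CAP-MP eligibility criteria beside the pilot's. If they already contain equivalents of list 7, one sentence saying so settles the point.
2. Where they differ, define the primary comparator as PUSH participants who meet items 7.1, 7.2, 7.3 and 7.7 wherever these were recorded, using screening or baseline records only. Fix the rule before pilot outcomes are compared.
3. State the resulting number of controls and the detectable difference for both comparisons.
4. Keep the full 105 (and 19) as a sensitivity analysis.
5. Name any criterion that CAP or CAP-MP did not record (possibly HbA1c) as a residual limitation.

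The cost is SAP wording, a filter on existing records and the loss of some controls: about 0.474 to 0.48 SD for CAP if 10-15% are removed, and proportionally more for CAP-MP. Alignment stays partial where data are missing. No change to pilot eligibility or treatment is involved.
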